5.8.1.4. Management of adverse effects attributed to study medication

During the trial, if a participant develops side effects thought to be due to the study medication and requires cessation of study medication, the medication will be stopped for 4 weeks. If the side effects disappear, an attempt will be made to reintroduce the study medication after 4 weeks. If the symptoms reappear, study medication will be once again stopped and the patient will no longer receive the study medication, but will be followed in the study according to the protocol, in keeping with the "intention-to-treat" paradigm.

5.8.2. Safety issues related to liver biopsy

Patients will have up to two liver biopsies for research purposes during their participation in this protocol. About 20% of people who have a liver biopsy have some degree of pain over the liver that may last a few minutes up to several hours. This occasionally requires pain medication and usually disappears completely within a day or two. A rare complication of liver biopsy is severe bleeding such that a blood transfusion or even radiological/surgical interventions are required to stop the bleeding (less than 1 in 1,000). Very rarely (less than 1 in 10,000 reported cases) death has occurred from bleeding after a biopsy. We intend to minimize the risks associated with liver biopsy (a) by requiring that each of the physicians who will obtain liver biopsies in the NASH CRN be very experienced in safely obtaining the liver biopsy specimens, (b) by not enrolling subjects with cirrhosis or subjects with coagulopathy, (c) by adhering to the good clinical practice in performing the liver biopsy, (d) by assuring that an attending hepatologist or radiologist directly supervises if a physician trainee is performing the procedure, and (e) by considering a transjugular liver biopsy in morbidly obese patients in whom a percutaneous, mid-axillary approach may not be feasible.

5.8.3. Safety issues related to patient privacy

It is the investigator's responsibility to conduct the protocol under the current version of Declaration of Helsinki, Good Clinical Practice, and rules of local IRBs. The investigator must ensure that the patient's anonymity be maintained in their data submission to the Data Coordinating Center. Patients will be identified only by an identification code but not by their name, SSN, or hospital medical record number. Investigators will maintain a separate confidential enrollment log which matches identifying codes with the patients' names and addresses (i.e., available only to local clinic staff). All study material will be maintained in strict confidence.

5.8.4. Safety issues related to specimen repository

It is anticipated that serum, plasma, DNA, and liver tissue from the participants will be stored for future studies related to NASH and possibly other liver/metabolic diseases. These samples will be stored in a central repository. The NASH CRN Steering Committee will develop specific guidelines addressing the issues such as (a) obtaining a separate informed consent, (b) storage, (c) transportation of the material, (d) who will have access to the material, and (e) what investigations to be conducted.

5.9. Adherence and retention

Two important goals of this protocol are to optimize adherence to the pharmacological regimen and to maximize the retention of participants in the study. Assessment of adherence to the assigned study medication will provide clinic staff a means to identify participants having problems with adherence. Adherence will be assessed by:

- Counts of pills in the patient's returned pill containers
- Conducting a brief, structured interview, in which the study coordinator will assist the patients to identify problems in taking the study medication and to estimate adherence to the prescribed medicine since their previous visit.

These assessments will guide the consideration of strategies to improve adherence. Resources will be provided to remove barriers to participation such as child or elder care, transportation, and parking expenses. These resources can be provided as cash, transportation vouchers, or parking passes.

An honorarium may be paid to patients in recognition of their time and effort twice during the trial when scheduled visits and procedures are completed successfully.

Certificates of appreciation may be given at enrollment and at conclusion as an incentive.

5.10. Management of concomitant conditions

Hypertension and hyperlipidemia will be managed in conjunction with the patient's primary care physician according to the protocols described in the Standards of Care document prepared by the Standards of Care Committee of NASH CRN.

Pregnancy and diabetes will be managed according to the guidelines shown in sections 5.8.1.1. and 5.8.1.2.

In the event of major dermatological reactions such as generalized urticaria, bullous rashes,

exfoliative dermatitis, or Stevens-Johnson Syndrome, study medication will be discontinued immediately and not restarted. For local skin reactions, study medication may be discontinued if the skin reactions are potentially drug related. If the rashes clear, the study medication may be restarted. If local skin reactions recur with restarting the study medication, study medication should be discontinued. In cases where the study medication has been discontinued, the study medication will be unmasked and the participant, investigator, and the primary care provider will be notified in order to prevent future exposures.

5.11. Food and Drug Administration

The PIVENS trial will be conducted under an Investigational New Drug (IND #69,751) held by the NIDDK Project Officer. The investigators will complete a Statement of Investigator (FDA Form 1572) per the Code of Federal Regulations before the initiation of the PIVENS trial. The safety data required to meet IND regulatory requirements will be collected through adverse event reporting by the clinic investigators and will be provided by the Data Coordinating Center to the NIDDK for transmission to the FDA.

5.12. Adverse event reporting

The PIVENS trial will monitor and report adverse events to ensure patient safety. There are two separate sets of government regulations that apply to unanticipated or adverse events in research studies: (1) 45 CFR Part 46, Subpart A; the "Common Rule", shared by 17 Departments and Agencies and (2) 21 CFR 312, the FDA regulation for adverse events. The Common Rule requires written procedures and policies for ensuring reporting of "unanticipated problems" involving risks to participants to IRBs, appropriate institutional officials, and the Department or Agency Head. The FDA regulation requires notification of the FDA and participating investigators of any adverse event associated with the use of a test article that is "both serious and unexpected." Since the definitions and reporting requirements for unanticipated events differ between the two sets of Federal regulations, the PIVENS trial definitions and procedures for adverse events are designed to satisfy both sets of requirements.

5.12.1. Definitions

Adverse event. An adverse event is any untoward medical occurrence that may present itself during treatment or administration with a pharmaceutical product or clinical procedure and which may or may not have a causal relationship with the treatment. Adverse events include any unanticipated problems involving risks to participants, or breaches of protocol which might entail risk to participants. The term "unanticipated problem" includes both new risks and increased rates of anticipated problems.

Serious adverse event. A serious adverse event (SAE) is an adverse event occurring at any time during the study that results in death, life-threatening adverse drug experience, inpatient hospitalization or prolongation of existing hospitalization, a persistent or significant disability/incapacity, or a congenital anomaly/birth defect. Other events may also be considered an SAE if, based on medical judgement, the event jeopardized the patient to the point of requiring medical or surgical intervention to prevent the occurrence of any of the conditions for an SAE listed above.

Unexpected adverse event. An unexpected adverse event is any adverse event with specificity or severity that is not consistent with the risk information in the study protocol, current investigator brochure, or current package insert.

Associated with the use of the drug means that there is a reasonable possibility that the adverse experience may have been caused by the drug.

5.12.2. Monitoring for adverse events

Adverse events will be recorded on study data forms whether or not they are thought to be associated with the study or with one of the study drugs. Adverse events may be discovered during regularly scheduled visits or through unscheduled patient contacts between visits.

Summary data on adverse events will be monitored by the DSMB quarterly and at its semiannual meetings or more frequently, as needed. These summaries will include analyses comparing rates of adverse events by treatment group, by clinic, or in other subgroups requested by the DSMB. Where applicable, signs and symptoms associated with the adverse event will be graded as to severity by the clinical site staff as mild, moderate, or severe using the Common Terminology Criteria for Adverse Events (65).

After each meeting, the DSMB will issue a written summary of its review of the study data, including adverse events, for transmission to the IRBs at each of the study centers. Analyses or listings of adverse events will not be provided to the IRBs; however, adverse events involving unanticipated problems involving risks to participants, or breaches of protocol which might entail risk to participants must be reported to local IRBs as soon as possible after they are discovered. Each participating center is responsible for ensuring that all local IRB requirements for reporting adverse events are met.

A summary of adverse events will be reported to the FDA as part of the IND annual report.

5.12.3. Reporting serious adverse events

Serious adverse events (SAE) must be reported upon discovery at the clinical center. This will involve completing an SAE data form describing the severity and details of the event. The SAE form, together with a memo summarizing the circumstances of the event and the current status of the patient, must be faxed to the Data Coordinating Center and to the NIDDK project officer within one working day of the discovery of the SAE. Also within one day, the clinical center must notify the NIDDK and Data Coordinating Center of the SAE by telephone or confirmed e-mail. The NIDDK project officer will work with the Data Coordinating Center to transmit the SAE form and memo to all study centers and to the DSMB.

If the SAE is unexpected AND associated with a study drug, then the NIDDK project officer will notify the FDA no later than 15 days from the discovery of the SAE (no later than 7 days if the SAE is fatal or life threatening). The pharmaceutical manufacturer will also be notified. The clinical center investigator may also be responsible for completing an FDA MedWatch 3500 form.

The DSMB will review each SAE report and provide comments to the NIDDK project officer within one week of receipt of the report. If requested by any member of the DSMB, a teleconference will be scheduled to discuss the SAE and recommend any actions to the NIDDK sponsor.

The clinical center must submit to the NIDDK project officer and to the Data Coordinating Center a follow-up memo within one month of the SAE (and periodic updates if needed) to report the details of the disposition of the SAE. The NIDDK project officer will work with the Data Coordinating Center to distribute the follow-up memo to the clinical center and to the DSMB.

5.13. Procedures for unmasking treatment assignment

Treatment assignments are double masked throughout the study until all data collection for the PIVENS trial has been completed (i.e., after completion of the 24 week post trial Follow-up for all patients). Every effort will be made to maintain the masking throughout the study except in emergency situations. The code of specific pharmacological treatment will not be broken without the knowledge of the clinical center's principal investigator.

Unmasking of study medication will occur under the following conditions:

- Severe allergic reaction (Stevens-Johnson Syndrome): Study medication is stopped indefinitely. The patient, primary care provider (PCP), and the investigator will be unmasked.
- **Pregnancy during the study**: Study medication will be stopped indefinitely, and the coded medication will be unmasked. The patient, PCP, and investigator will be notified of the assigned treatment and the associated risks of teratogenicity.
- **Development of hepatotoxicity**: Study medication will be discontinued according to the guidelines in section 5.8.1.1. The patient, PCP, and the investigator will be unmasked.
- **New onset diabetes**: The patient will be referred to their PCP and managed according to the stepped care approach defined in section 5.8.1.2. The patient and PCP may be unmasked to the study medication but the investigator will continue to be masked.

In unforeseen situations where the clinical center principal investigator considers unmasking is in the best interest of the participant's health and well being, unmasking may be done after notifying the Executive Committee.

The Data and Safety Monitoring Board will review all instances of unmasking that occur.

6. Statistical design and analysis

6.1. Hypotheses

Primary hypotheses:

- In nondiabetic adult patients with NASH, improvement in insulin resistance over 96 weeks of treatment with pioglitazone, compared to treatment with placebo, will result in improvement in NASH disease activity as assessed by a histologic score comprised of steatosis, lobular inflammation, and cellular ballooning
- In nondiabetic adult patients with NASH, improvement in oxidative stress status over 96 weeks of treatment with vitamin E, compared to treatment with placebo, will result in improvement in NASH disease activity as assessed by a histologic score comprised of steatosis, lobular inflammation, and cellular ballooning

Secondary hypotheses:

- Pioglitazone and vitamin E are equally effective in achieving histologic improvement in nondiabetic patients with NASH
- Levels of proinflammatory cytokines, serum markers for fibrosis will decrease with treatment with pioglitazone and with vitamin E compared to treatment with placebo
- Nondiabetic adult patients with NASH have an impaired quality of life, and these scores will improve as their liver histology improves upon treatment with pioglitazone or vitamin E, compared to treatment with placebo

Other questions to be addressed:

- We predict that insulin resistance is common in nondiabetic adult patients with NASH and will be significantly related to waist-to-hip ratio, waist circumference, and hepatic histology
- We predict that degree of obesity will be significantly related to hepatic histology in nondiabetic patients with NASH and more severe obesity will be related to more advanced hepatic histology

- We predict that age will be significantly related to hepatic histology in nondiabetic adult patients with NASH and older individuals will have more advanced hepatic histology
- We predict that serum markers for fibrosis will be significantly related to hepatic histology in nondiabetic adult patients with NASH
- We predict worsening hepatic histology will be significantly related to a worsening in health-related quality of life in nondiabetic adult patients with NASH and more advanced histology will have worse health-related quality of life as measured by scores on the modified SF-36
- We predict that improvement in the measures of insulin resistance will be significantly related to improvements in liver histology and serum markers for fibrosis in adult nondiabetic patients with NASH
- We predict that therapy with vitamin E will improve insulin resistance in adult nondiabetic patients with NASH
- We predict that improvement in liver histology upon treatment with insulin sensitizers will be significantly related to improvements in waist-to-hip ratio and waist circumference in adult nondiabetic patients with NASH

6.2. Outcome measures

Primary outcome measure:

The primary outcome measure requires improvement in NASH activity after 96 weeks of treatment as determined by liver biopsies pre- and post-treatment. The measure is derived from changes from baseline to the end of treatment in the NASH CRN NAFLD/NASH activity score (NAS). The NAS ranges from 0 to 8 (highest activity) and is calculated as the sum of three components of the standardized histologic feature scoring system for liver biopsies:

NAS	=	Steatosis score $(0-3) +$
		Lobular inflammation score $(0-3) +$
		Hepatocyte ballooning score (0-2)

As noted earlier, a NAS of 5 or greater with each subscore at least 1 or a NAS of 4 with each subscore at least 1 and a finding of definite steatohepatitis by at least two of three NASH CRN pathologists is a requirement for enrollment into the trial.

38

The definition of improvement after treatment as the primary outcome measure requires the following three conditions:

- No worsening of the fibrosis feature score
- Improvement by at least 1 point in the hepatocyte ballooning feature score
 - Either: (1) Improvement in NAS by 2 or more points spread across at least two of the NAS components, OR
 - (2) Post-treatment NAS is 3 points or less

Secondary outcome measures:

- Change in NAS after 96 weeks of treatment compared to baseline NAS. Mean changes in NAS will be compared.
- Changes in fibrosis, steatosis, lobular inflammation, cellular ballooning and other specific features from the histologic scoring system after 96 weeks of treatment compared to baseline. Improvement in specific features will be defined as any improvement in the score. Mean changes will also be compared.
- Change in serum aminotransferase levels after 96 weeks of treatment compared to baseline. A biochemical response is considered a fall of ALT levels into the normal range. Patients are not required to have abnormal levels of aminotransferases in order to enter this trial as long as they meet histological and other clinical criteria. Therefore, patients with normal levels of transaminases may be enrolled. If an adequate number of such patients are enrolled, a subgroup analysis will be performed.
- Change in anthropometric measurements (weight, BMI, waist-to-hip ratio, waist circumference, triceps skin fold thickness and total body fat) after 96 weeks of treatment compared to baseline.
- Change in insulin resistance (assessed by HOMA), serum vitamin E levels, cytokines, fibrosis markers, and lipid profile after 96 weeks of treatment compared to baseline.
- Change in health-related quality of life (SF-36) after 96 weeks of treatment compared to baseline.

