4.2. Inclusion criteria

In order to qualify for inclusion in the trial, patients must satisfy the following inclusion criteria:

Based on a liver biopsy obtained no more than 6 months prior to randomization (patient must not have used antiNASH medications in the 3 months prior to the biopsy), histological evidence of NASH as defined by a NASH activity score, which is EITHER (1) a composite score of 5 or greater (where each component score for steatosis, hepatocyte ballooning, and lobular inflammation is 1 or more) as judged by the local NASH CRN pathologist with a finding of possible (defined as suspicious/borderline/indeterminate) or definite steatohepatitis as judged by the local NASH CRN pathologist, OR (2) a composite score of 4 (where each component score for steatosis, hepatocyte ballooning, and lobular inflammation is 1 or more) as judged by the local NASH CRN pathologist and a finding of definite steatohepatitis as judged by the local NASH CRN pathologist and a finding of definite steatohepatitis as judged by the local NASH CRN pathologist and a finding of definite steatohepatitis as judged by the local NASH CRN pathologist and a finding of definite steatohepatitis as judged by the local NASH CRN pathologist and a finding of definite steatohepatitis as judged by the local NASH CRN pathologist and two additional NASH CRN pathologists (i.e., at least two of the three pathologists must find definite steatohepatitis).

17

2. Patient must be 18 years of age or older as of the initial screening interview.

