5.7. Overview of scoring of liver biopsies

The tissue will be examined by light microscopy and scored based upon the NASH CRN NAFLD/NASH scoring system. The scoring system is detailed in the Liver Biopsy Procedure and NAFLD/NASH Histologic Scoring System Manual prepared by the NASH CRN Pathology Committee and approved by the NASH CRN Steering Committee. Briefly, biopsies will be assessed for the following:

- (1) Adequacy of the biopsy sample for reading;
- (2) Steatosis (including grade of 0-3, location, and whether microvesicular);
- (3) Fibrosis based upon Masson's trichrome stain as 0-4 with: 0 = none
 1a = mild zone 3 perisinusoidal
 1b = moderate zone 3 perisinusoidal
 1c = portal/periportal only
 2 = zone 3 and periportal
 3 = bridging
 4 = cirrhosis
- (4) Lobular inflammation as 0, 1 (<2 areas seen), 2 (2-4 areas seen), or 3 (>4 areas seen under 20-fold magnification) and as presence or absence of microgranulomas and lipogranulomas
- (5) Portal inflammation as 0 (none), 1 (mild), or 2 (greater than mild)
- (6) Liver cell injury: Ballooning as 0 (none), 1 (few) and 2 (many), with notation of presence or absence of acidophilic bodies (0 =rare or 1 = many), pigmented macrophages (0 = rare/absent, 1 = many), and megamitochrondria (0 = rare/absent, 1 = many)

5. Trial protocol

- (7) Mallory bodies as 0 (rare/absent) or 1 (many)
- (8) Glycogen nuclei as 0 (rare/absent) or 1 (many)
- Hepatocellular iron grade based on iron stain as 0 (absent or barely discernible, 40x), 1 (barely discernable granules, 20x), 2 (discrete granules resolved, 10x), 3 (discrete granules resolves, 4x), and 4 (masses visible by naked eye)
- (10) Steatohepatitis finding (No; Suspicious/borderline/indeterminate; or Yes, definite)

The component scores will be used to determine eligibility as well as primary histologic outcome measure defined elsewhere in this protocol. Baseline liver biopsies will be scored by the local NASH CRN pathologist for eligibility. Baseline and follow-up liver biopsies will be scored by central review of the slides by the Pathology Committee. The scores obtained centrally will be used for data analysis.

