6.3. Statistical analysis

Primary hypotheses:

Statistical analyses for the two primary hypotheses will follow the intention-to-treat paradigm, which means that all randomized patients with baseline and 96 week liver biopsies will be included in the treatment group to which they were assigned. Any randomized patient who does not have the requisite biopsies will be accounted for and compared by assigned treatment group. Patients not able

to be included in the intention-to-treat analyses will be compared to those who are included with respect to demographic and other characteristics.

Since the primary outcome measure, defined in Section 6.2, is a binary indicator of improvement in histologic activity score after 96 weeks of treatment compared to baseline and since the randomization is stratified by clinic, P-values will be derived from the Mantel-Haenszel χ^2 test for stratified 2x2 tables (66). Two P-values will be derived: one comparing proportions improved in the group assigned to pioglitazone compared to the group assigned to placebo and another comparing the group assigned to vitamin E to the group assigned to placebo. Since two primary comparisons are planned, a P-value of 0.025 will be considered significant, applying a Bonferroni correction for multiple comparisons.

Given the randomized design and adequate size planned for the PIVENS trial, it is unlikely that confounding of the treatment groups by covariates related to the change in histologic activity score will occur. However, if confounding should occur, logistic regression analyses with histologic improvement as the binary response and treatment group indicator and any suspected confounders as covariates will be carried out to determine the sensitivity of the primary P-value to confounding.

Secondary hypotheses:

The first secondary hypothesis, that pioglitazone and vitamin E are equally effective in achieving histologic improvement, involves the primary outcome measure. Equivalence will be assessed in two ways: (1) a formal test for equivalence, testing that the difference between proportions improved in the pioglitazone and vitamin E groups does not exceed 10% and (2) 95% confidence intervals on the difference in proportions improved.

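### Entry guarantees ballooning of 1 or more only on the local reading, so a patient read centrally as 0 at baseline cannot meet the primary outcome, and the planned test makes no allowance for this

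*Protocol*

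**What the plan says.** Section 4.2 sets the histological entry score, "where each component score for steatosis, hepatocyte ballooning, and lobular inflammation is 1 or more) as judged by the local NASH CRN pathologist". Section 5.7 repeats the assignment of readers: "Baseline liver biopsies will be scored by the local NASH CRN pathologist for eligibility". It then gives the analysis to a different reading: "Baseline and follow-up liver biopsies will be scored by central review of the slides by the Pathology Committee", and "The scores obtained centrally will be used for data analysis".

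Section 6.2 defines the primary outcome: "The definition of improvement after treatment as the primary outcome measure requires the following three conditions". They are no worsening of fibrosis, "Improvement by at least 1 point in the hepatocyte ballooning feature score", and a third condition with two alternatives: (1) a fall in NAS of at least 2 points spread over at least two components, or (2) a post-treatment NAS of 3 or less. The choice lies inside the third condition and does not waive the ballooning condition. Ballooning is scored from 0 to 2.

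Section 6.3 analyses all randomized patients who have both biopsies. On the test it says: "since the randomization is stratified by clinic, P-values will be derived from the Mantel-Haenszel" χ² test. Section 6.4 counts missing outcomes as unimproved. No section requires central confirmation of ballooning before randomization, or gives patients read centrally as ballooning 0 another response definition.

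**The concern.** The entry rule and the endpoint fit together only if the local and central readings agree that ballooning is present. Where they disagree, with local 1 or more and central 0, the patient starts at the floor of the central scale and cannot improve on a mandatory component.

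At stake is precision in both primary comparisons. Patients with a fixed outcome carry no information on treatment. They dilute the response rates and, if they fall unevenly between arms by chance, they shift the estimated difference. The planned test is stratified by clinic only, so it takes no account of a baseline score that identifies these patients exactly.

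**Working it through.** **Logic.** Central ballooning at baseline is 0 and the scale cannot go below 0, so the largest possible fall is 0, which is less than 1. The second condition fails and all three are required. The response probability is exactly 0 in every arm. The extra review at NAS 4 (at least two of three pathologists finding definite steatohepatitis) concerns the diagnosis. It does not guarantee a central ballooning score of 1 or more, and it does not apply at NAS 5 or more.

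**The plan's own figure.** Inputs from 6.5: π₁ = 0.14, π₂ = 0.40, mean 0.27, two-sided α = 0.025, power 90%.

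n = [2.2414·√(2·0.27·0.73) + 1.2816·√(0.14·0.86 + 0.40·0.60)]² / 0.26² = 70.08, rounded up to 71. Then 71/0.9 = 78.9, that is 79, which the protocol takes as approximately 80. The arithmetic reproduces.

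**Effect of a share f with central baseline ballooning 0.** The protocol does not give f, so the values below are assumptions. Two readings of the planning rates are possible.

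*Reading A: 0.14 and 0.40 apply only to patients able to respond.* Each group rate is multiplied by (1 − f), and the difference becomes 0.26·(1 − f). At f = 10% the rates are 0.126 and 0.36; at f = 20% they are 0.112 and 0.32. The protocol's formula, solved for power at 71 per group, gives 90.4% (f = 0), 88.0% (5%), 85.3% (10%), 78.7% (20%) and 74.9% (25%).

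The planned clinic-stratified test was also simulated: 8 clinics with 9 patients per arm each, so 72 per arm, which is 80 less 10%. Ranges are over repeated runs.

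| f | Stratified by clinic only | Clinic and central ballooning (0 vs 1 or more) |
|---|---|---|
| 0 | 91% | 91% |
| 5% | 89% | about 0.5 points higher |
| 10% | 86–87% | 87–88% |
| 20% | 80–81% | 83% |
| 25% | 76–77% | 80% |

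*Reading B: 0.14 and 0.40 are group-wide rates that already include these patients.* Simulated power of the clinic-only test is about 91% at f = 0, 10%, 20% and 25%. Adding the ballooning stratum again gains about 0.5 to 3 points over f = 5–25%.

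**Type I error.** It was 0.022–0.026 with clinic strata only and 0.023–0.026 with the added stratum.

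**Chance imbalance.** At f = 20% and 80 per arm, the standard deviation of the between-arm difference in f is √(2·0.2·0.8/80) = 0.063. An imbalance of 10 points or more in either direction therefore has probability of about 11%. If it lay wholly in an active arm, it would move the response difference by up to 0.10 × 0.40 = 4 points. The standard error of the response difference there (rates 0.112 and 0.32) is √[(0.112·0.888 + 0.32·0.68)/80] = 0.063, so this shift is about 0.6 of a standard error.

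**Alternative (2).** Take central baseline scores of steatosis 1, inflammation 1 and ballooning 1 (NAS 3). If ballooning falls to 0 and steatosis rises to 2, NAS is still 3. With fibrosis no worse, the patient counts as improved with no net fall in NAS.

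**The case against.** Three stronger readings are tempting, and the protocol supports none of them.

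- **That power is certainly below 90%.** Section 6.5 describes 0.14 and 0.40 as the expected proportions improved in each group. Read literally these are group-wide, and power then stays at about 91% whatever f is. The loss arises only under reading A, and the protocol does not say which patients its pilot sources covered. Nor does anything in it support a particular f. Local readers are NASH CRN pathologists, scoring is on a common system with a manual, and entrants at NAS 4 receive additional diagnostic review. These features limit disagreement without ruling it out.
- **That imbalance biases the comparison or manufactures an effect.** The baseline biopsy precedes treatment, so randomization balances these patients in expectation. What remains is ordinary chance variation, which the significance level covers; simulated type I error stays at about 0.025.
- **That a patient with central baseline NAS of 3 or less responds automatically through alternative (2).** The ballooning fall and the fibrosis condition still apply. NAS can fail to drop only when a ballooning fall is offset by worsening steatosis or inflammation.

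It can also be said that an added stratum belongs in an SAP, that the power gain is small, and that 6.3 already offers logistic regression. The gain is indeed small. But the protocol itself fixes the endpoint, the readers, the population and the test, and the conflict lies between those. The logistic regression is conditional on confounding being suspected, names no covariates and serves only as a sensitivity check. It does not deal with an outcome that is known in advance to be fixed.

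**Conclusion.** The point stands at moderate severity. It follows from 4.2, 5.7, 6.2 and 6.3 read together that any patient with central baseline ballooning 0 is a certain non-responder, and this needs no assumed figure. The number affected is unknown.

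The cost to power ranges from nothing (group-wide planning rates) to a fall from about 91% to 89%, 86%, 81% and 77% at assumed f of 5%, 10%, 20% and 25% (rates restricted to patients able to respond). The validity of the test is not in question. What is lost is efficiency and protection against chance imbalance, both partly recoverable from a score already being collected. The gap in alternative (2) is a corner case and not a main defect.

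**What to change.** 1. In 6.3, specify before unmasking that the primary Mantel-Haenszel test is stratified by clinic and central baseline ballooning (0 versus 1 or more). No patient leaves the analysis set, although the zero stratum contributes nothing to the test statistic.
2. Report response rates among patients with central baseline ballooning of 1 or more as a supporting estimate.
3. In 6.5, state whether 0.14 and 0.40 include patients with central ballooning 0. If they do not, give power over a range of f.
4. Optionally, add to alternative (2) in 6.2 that the post-treatment NAS must also be lower than the baseline NAS.

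The cost is wording and one extra stratum; the central baseline scores are already planned. The strata become somewhat sparser: each pairwise comparison has about 2 × 72/8 = 18 evaluable patients per clinic, now divided in two. The stratum recovers only part of any loss and does not by itself restore 90% under reading A, so the stated power may become less favourable.
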